### **Safety Outcomes**

1. Intradialytic hypotensive episodes
2. Intradialytic hypertensive episodes
3. Intradialytic new onset cardiac arrhythmias including supraventricular tachycardia, bradycardia, atrial fibrillation, ventricular tachycardia, ventricular fibrillation, and cardiac arrest
4. Emergent use of rescue UFNET with rates higher than the assigned treatment arm
5. Severe hypophosphatemia (<0.5 mg/dL)
6. Severe hypokalemia (<3.0 mg/dL)
7. Severe hypocalcemia (<1.90 mg/dL or ionized calcium <0.90 mmol/L)
8. CKRT system downtime due to filter clotting or clogging
9. Discontinuation of UFNET due to hemodynamic instability
10. Inability to close surgical wounds due to edema
11. New organ dysfunction
12. Worsening of systolic or diastolic cardiac function on echocardiogram
13. Worsening of pulmonary edema on chest X Ray and/or CT scan
14. Worsening of ileus on abdominal X Ray and/or CT scan
15. Bowel ischemia or anastomotic breakdown based on intraoperative findings
16. Pressure ulcerations
17. New wound infections
18. New arterial or venous thrombosis
19. Severe anemia requiring red cell transfusions
20. Severe thrombocytopenia requiring platelet transfusions
21. New secondary infections

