#### 5.8.3 SAFETY OUTCOMES

1. Intradialytic hypotensive episodes
2. Intradialytic hypertensive episodes
3. Intradialytic new onset cardiac arrhythmias including supraventricular tachycardia, bradycardia, atrial fibrillation, ventricular tachycardia, ventricular fibrillation, and cardiac arrest
4. Emergent use of rescue UFNET with rates higher than the assigned treatment arm
5. Severe hypophosphatemia (<0.5 mg/dL)
6. Severe hypokalemia (<3.0 mg/dL)
7. Severe hypocalcemia (<1.90 mg/dL or ionized calcium <0.90 mmol/L)
8. CKRT system downtime due to hemofilter clotting or clogging
9. Discontinuation of UFNET due to hemodynamic instability
10. Inability to close surgical wounds due to edema
11. New organ dysfunction
12. Worsening of systolic or diastolic cardiac function on echocardiogram
13. Worsening of pulmonary edema on chest X Ray and or/or CT scan
14. Worsening of ileus on abdominal X Ray and/or CT scan
15. Bowel ischemia or anastomotic breakdown based on intraoperative findings
16. Pressure ulcerations
17. New wound infections
18. New arterial or venous thrombosis
19. Severe anemia requiring red cell transfusions
20. Severe thrombocytopenia requiring platelet transfusions
21. New secondary infections

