### 7.4.3 CKRT PROCEDURES

We will follow specific protocols for management of CKRT to ensure uniformity of treatment between the patient groups. We have chosen CKRT as the primary modality for  $UF_{NET}$  for this trial because (i) overall volume control is superior with CKRT compared with IHD, (ii) better hemodynamic tolerance than IHD in critically ill patients, (iii) more than 70% of critical care practitioners surveyed use CKRT for volume removal, (iv) primary modality used for treatment in ICU patients with severe fluid overload and multisystem organ failure at the UPMC and the Mayo Clinic ICUs.

CKRT will be provided at the discretion of attending nephrologist ([Appendix D](#)). CKRT modality will either be CVVHDF, CVVHD, CVVH or SCUF. All hemofilters will be comprised of biocompatible synthetic hollow-fiber membranes and will be changed at least every 48-72 hours. The electrolyte composition of the dialysate and replacement fluids and dialysate and replacement fluid flow rates will be prescribed by the attending nephrologist. Dialysate will be bicarbonate-buffered. Choice and type of anticoagulation will be at the discretion of

the clinician. Effluent flow rate will be 20-30 mL/kg/h and prescribed by the attending nephrologist. All efforts will be made to minimize CKRT downtime and ensure that CKRT is functioning at least 20 hours per day. Patients would be transitioned from CKRT to IHD or no KRT as determined by the treating physicians.

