## 13 SAFETY MONITORING

### 13.1 ADVERSE EVENTS

A clinical trial adverse event (AE) is defined as any untoward medical event temporally associated with the use of drug or study procedure in humans, whether or not it is considered related to a study intervention or study procedure. Assuring patient safety is an essential component of this protocol and the Principal Investigators have the primary responsibility for the safety of the individual participants. Thus, the Principal Investigators

will monitor for all AEs from study enrollment until ICU discharge or day 28, whichever occurs first.

Following study enrollment, AEs occurring after the patient received the study interventions will be evaluated at the two clinical sites by the Principal Investigators. Investigators will assess if there is a reasonable possibility that the study procedure caused the event, based on the criteria outlined in [Appendix G1](#).

If a patient's study treatment is discontinued because of an AE, the study investigator must report the circumstances and data leading to discontinuation of treatment in the AE case report forms. AEs will be considered related or possibly related to study treatment only up to 24 hours following discontinuation of CKRT. AEs occurring after discontinuation of CKRT and after transition to IHD will not be considered related to study interventions.

Investigators will also consider if the event is unanticipated or unexplained given the patient's clinical course, previous medical conditions, and concomitant medications as outlined in [Appendix G2](#). An adverse event is considered "unanticipated" if it is not listed in the study protocol (21 CFR 312.32(a)).

The following adverse events will be collected in the case report forms:

- Serious adverse events
- Non-serious adverse events that are considered by the investigator to be related to study intervention or study procedures or of uncertain relationship ([Appendix G](#))
- New onset hypotensive and hypertensive episodes, cardiac arrhythmias, considered by the investigator to be related to rate of fluid removal during CKRT, or of uncertain relationship
- Emergent use of rescue UFNET rates with rates higher than the assigned treatment arm
- Severe hypophosphatemia, hypokalemia, hypocalcemia
- CKRT system clotting, clogging, downtime, and discontinuation of fluid removal due to patient instability.
- Inability to close surgical wounds due to edema

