We will also assess safety outcomes such as intradialytic hypotensive and hypertensive episodes; cardiac arrhythmias; emergent use of rescue  $UF_{NET}$  rates higher than the assigned group for treatment of fluid overload; severe hypophosphatemia, hypokalemia, and hypocalcemia; CKRT circuit downtime due to filter clotting or clogging; discontinuation of fluid removal due to hemodynamic instability; inability to close surgical wounds due to edema; new organ dysfunction; diastolic and systolic dysfunction; pulmonary edema; ileus, bowel ischemia, anastomotic break down; pressure ulceration; wound infections; arterial or venous thrombosis; severe anemia requiring red cell transfusion, severe thrombocytopenia requiring platelet transfusions; and secondary infections.

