#### 3.5.3 SAFETY OUTCOMES

1. No. of intradialytic hypotensive episodes
2. No. of intradialytic hypertensive episodes
3. No. of intradialytic new onset cardiac arrhythmias including supraventricular tachycardia, bradycardia, atrial fibrillation, ventricular tachycardia, ventricular fibrillation, and cardiac arrest
4. No. of participants with emergent use of rescue  $UF_{NET}$  with rates higher than the assigned treatment arm
5. No. of participants with severe hypophosphatemia ( $<0.5$  mg/dL)
6. No. of participants with severe hypokalemia ( $<3.0$  mg/dL)
7. No. of participants with severe hypocalcemia ( $<1.90$  mg/dL or ionized calcium  $<0.90$  mmol/L)
8. No. of episodes of stopping CKRT due to filter clotting or clogging
9. No. of participants with discontinuation of  $UF_{NET}$  due to hemodynamic instability
10. No. of participants in whom surgical wounds are left open due to edema
11. No. of participants with new organ dysfunction
12. No. of participants with worsening of systolic or diastolic cardiac function on echocardiogram
13. No. of participants with worsening of pulmonary edema on chest X Ray and/or CT scan
14. No. of participants with worsening of ileus on abdominal X Ray and/or CT scan
15. No. of participants with bowel ischemia or anastomotic breakdown based on intraoperative findings
16. No. of participants with pressure ulcerations
17. No. of participants with new wound infections
18. No. of participants with new arterial or venous thrombosis
19. No. of participants with severe anemia requiring red cell transfusions

20. No. of participants with severe thrombocytopenia requiring platelet transfusions
21. No. of participants with new secondary infections

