## 5 APPENDICES

### 5.1 APPENDIX A: OUTCOME VARIABLES AND ANALYSIS METHOD

Variable	Outcome Category	Scale	Analysis Method
Between-group separation in mean delivered UF NET rates	Primary	Continuous	GLMM
Protocol deviation	Primary	Binary	Wald-test for GLMM
Recruitment rate	Primary	Continuous	GLMM
Daily fluid balance	Secondary	Continuous	GLMM
Cumulative fluid balance	Secondary	Continuous	GLMM
Duration of kidney replacement therapy	Secondary	Continuous	GLMM
Duration of mechanical ventilation	Secondary	Continuous	GLMM
Organ failure free days	Secondary	Continuous	GLMM
ICU length of stay	Secondary	Continuous	GLMM
Hospital length of stay	Secondary	Continuous	GLMM
Hospital mortality	Secondary	Binary	Wald-test for GLMM
Dialysis dependence at hospital discharge	Secondary	Binary	Wald-test for GLMM
Hypotensive episodes	Safety	Continuous	GLMM
Hypertensive episodes	Safety	Continuous	GLMM
Cardiac arrhythmias	Safety	Continuous	GLMM
Emergent use of rescue UF NET rates	Safety	Binary	Wald-test for GLMM
Severe hypophosphatemia	Safety	Binary	Wald-test for GLMM
Severe hypokalemia	Safety	Binary	Wald-test for GLMM
Severe hypocalcemia	Safety	Binary	Wald-test for GLMM
CKRT stopping due to hemofilter clotting or clogging	Safety	Continuous	GLMM
Discontinuation of fluid removal due to hemodynamic instability	Safety	Binary	Wald-test for GLMM
Inability to close surgical wounds	Safety	Binary	Wald-test for GLMM
New organ dysfunction	Safety	Binary	Wald-test for GLMM
Worsening systolic/diastolic cardiac function	Safety	Binary	Wald-test for GLMM

Worsening pulmonary edema	Safety	Binary	Wald-test for GLMM
Worsening of ileus	Safety	Binary	Wald-test for GLMM
Bowel ischemia or anastomotic breakdown	Safety	Binary	Wald-test for GLMM
Pressure ulcerations	Safety	Binary	Wald-test for GLMM
New wound infections	Safety	Binary	Wald-test for GLMM
New arterial or venous thrombosis	Safety	Binary	Wald-test for GLMM
Severe anemia	Safety	Binary	Wald-test for GLMM
Severe thrombocytopenia	Safety	Binary	Wald-test for GLMM
New secondary infections	Safety	Binary	Wald-test for GLMM

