5.3.3 TABLE 3: SAFETY OUTCOMES

Safety Outcomes	Restrictive		Liberal		Unadjusted P value	Adjusted P value §
	No. of Patients (%)	No. of episodes	No. of Patients (%)	No. of episodes		
Intradialytic hypotension						
Intradialytic hypertension						
Cardiac arrhythmias						
Use of rescue net ultrafiltration						
Hypophosphatemia (<0.5 mg/dL)						
Hypokalemia (<3.0 mg/dL)						
Hypocalcemia (<1.90 mg/dL)						
Hemofilter clotting or clogging						
UF NET discontinuation due to instability						
Surgical wounds edema						
New organ dysfunction						
Worsening cardiac function						
Worsening of pulmonary edema						
Worsening of ileus						
Bowel ischemia or anastomotic breakdown						
New pressure ulcerations						
New wound infections						
New arterial or venous thrombosis						
Severe anemia						
Severe thrombocytopenia						
New secondary infections						

§ Adjusted for differences in age, baseline eGFR, APACHE-III score, Elixhauser Comorbidity Index score, mechanical ventilation, admission source, percentage of fluid overload, sepsis, and baseline cardiovascular SOFA score. P values are for the between-group differences in the percentage of patients with a specific event and have not been adjusted for multiple comparisons.

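### The SAP analyses stops of CKRT for clotting, not the CKRT downtime that the protocol names as safety outcome 8 and the SAP's own summary repeats

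*Protocol*

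**What the plan says.** **Protocol.** Safety outcome 8 is "CKRT system downtime due to filter clotting or clogging" in the trial summary (section 4) and "CKRT system downtime due to hemofilter clotting or clogging" in section 5.8.3. The executive summary (section 3) names downtime too. Section 13.1 collects "CKRT system clotting, clogging, downtime, and discontinuation of fluid removal due to patient instability". Appendix F2 schedules clogging, clotting and downtime as separate complications, and hours of therapy among the CKRT data. Section 7.4.3 couples minimising downtime with the aim to "ensure that CKRT is functioning at least 20 hours per day".

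**SAP.** The trial summary (section 3) says the safety outcomes to be assessed include "CKRT circuit downtime due to filter clotting or clogging". The parts that govern the analysis differ:

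- Section 3.5.3, item 8: "No. of episodes of stopping CKRT due to filter clotting or clogging".
- Appendix A: "CKRT stopping due to hemofilter clotting or clogging", classed as continuous and analysed by GLMM.
- Shell Table 3: one row for hemofilter clotting or clogging, with columns for patients (%) and episodes. Its footnote says "P values are for the between-group differences in the percentage of patients with a specific event".

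**The concern.** The protocol names an outcome that, on its own usage, is time off therapy. The SAP counts events or classifies patients as having had one. If the SAP is followed as written, the report will contain no result for the named outcome, and the row standing in its place will give equal weight to a brief filter change and a gap of many hours.

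This matters more here than in most trials. The question is whether an assigned rate of fluid removal can be delivered, and protocol Appendix D links delivery of the intended dose to keeping time off CKRT short. Hours lost to circuit failure in each arm would help in planning the phase III trial.

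**Working it through.** There is no stated figure to reproduce. The check is mainly a comparison of texts, followed by one piece of arithmetic on what the change of measure could do.

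**1. The places side by side**

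| Place | Content | Measure |
|---|---|---|
| Protocol 3, 4 and 5.8.3 | Downtime from clotting or clogging | No unit given |
| Protocol 13.1 | Clotting, clogging and downtime as distinct items | Collected |
| Protocol Appendix F2 | The same three items, plus hours of therapy | Collected |
| SAP 3 | Downtime from clotting or clogging | No unit given |
| SAP 3.5.3, item 8 | Stopping episodes | Count |
| SAP Appendix A | CKRT stopping | Continuous, GLMM |
| SAP Appendix B | No derivation of downtime or of stops | None |
| SAP Table 3 | Clotting or clogging | Patients (%) and episodes; P value for the percentage |

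No SAP row measures time. Appendix A and Table 3 also disagree with each other on what is tested: a continuous stopping variable in one, any event per patient in the other.

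**2. Is downtime a time?** The protocol gives outcome 8 no unit, so this has to be inferred. Section 7.4.3 pairs downtime with hours of function per day. Appendix D speaks of the periods when the patient is off CKRT. Section 13.1 and Appendix F2 list downtime apart from clotting and clogging, so it is not a synonym for either. Together these support reading it as time off therapy.

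**3. Is the information recovered elsewhere?** Not by the primary analysis. SAP 4.2.1 leaves hours without fluid removal out of the patient-averaged rate, so hours lost to clotting do not lower that average. No other listed outcome measures time lost to circuit failure.

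**4. Could stops and hours disagree?** Write hours lost as H = n × d, with n stops and d mean hours per stop. If arm A has more stops, arm B still loses more hours when d_B / d_A > n_A / n_B. The documents give neither n nor d, so the values below are assumptions. As a rough ceiling, the 20-hour aim leaves 24 − 20 = 4 h per day; over the four-day average course in protocol 5.2.8 that is 4 × 4 = 16 h. That allowance covers interruptions of every cause.

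| Stops, A v B | Hours per stop, A v B | Hours lost, A v B | Order by hours |
|---|---|---|---|
| 4 v 2 | 1 v 1 | 4 v 2 | Same as stops |
| 4 v 2 | 1 v 2 | 4 v 4 | Tie |
| 3 v 2 | 1 v 2 | 3 v 4 | Reversed |
| 4 v 2 | 1 v 4 | 4 v 8 | Reversed |

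The two measures are therefore not interchangeable. Whether they would differ in this trial cannot be told from the documents.

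**The case against.** **The SAP may define the metric.** Most of the 21 safety outcomes in the protocol are bare labels, protocol section 9 leaves statistical detail to the SAP, and SAP 3.5.3 gives every item a countable form. Counting stops is a defensible way to handle a safety event, and that much stands. It does not explain why SAP section 3 keeps downtime, or why the protocol collects downtime separately from clotting and clogging.

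**The SAP may simply be older.** It carries other design figures (144 patients in 6 ICUs, against 112 in 10 in the protocol). But this conflict also lies inside the SAP, between section 3 and section 3.5.3, and updating the design figures would not remove it.

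**The stakes are limited.** Protocol 11.3 says the trial is not powered for differences in adverse events, Table 3 makes no multiplicity adjustment, and no primary outcome or stopping rule in the documents uses this outcome. All of this stands and limits the size of the point.

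**The hours may not be available by cause.** This stands. Appendix F2 lists downtime and hours of therapy but shows no duration-by-cause field. Appendix D says patients also come off CKRT for scans and procedures, so hours of therapy alone cannot isolate clotting. The daily reference measurements in protocol 8.3.2 record interruption of CKRT only as yes or no.

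**Stronger readings.** A reader might infer that the SAP will rank the arms in the wrong order. The documents do not support that: they give no stop counts or durations and no reason why hours per stop should differ between arms. A reader might also infer that the SAP reports nothing but stops; Table 3 also shows the number and percentage of patients.

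**Conclusion.** The concern holds. Safety outcome 8 as named has no analysis in the SAP: it is replaced by stopping episodes in section 3.5.3 and Appendix A, and by the percentage of patients for the P value in Table 3. The conclusion rests on reading downtime as time off therapy, which the protocol's usage supports but no definition states. It does not rest on any assumed number.

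The size is one of 21 safety outcomes, with no effect on the primary outcomes. Disagreement between stops and hours is possible but not shown to be likely. The point should be corrected before analysis because the named outcome bears on whether treatment can be delivered, and because the correction is small.

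**What to change.** 1. In SAP 3.5.3 item 8, Appendix A, Appendix B and Table 3, define and analyse CKRT downtime due to clotting or clogging as hours per CKRT day. Keep the number of stops and patients (%) as supporting rows.
2. State in Table 3 which quantity its P value tests for this row, so that it agrees with Appendix A.
3. Name a model that accepts zero hours. The zero-truncated negative binomial that SAP 4.3 gives for continuous variables does not.
4. The sponsor should confirm that the Appendix F2 downtime entry records both duration and cause. If it does not, report all-cause downtime from the F2 hours of therapy, labelled as all-cause, next to the clotting stop count. Then make the outcome name in the protocol and in SAP section 3 match what is analysed.

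The sponsor could instead rename the outcome as a count throughout. That would reconcile the documents but leave time lost unmeasured.

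**Cost:** SAP wording, one more derived variable, and possibly a small clarification to an existing form field. Whether any additional collection is needed depends on the answer to item 4.

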## 13.2 SERIOUS ADVERSE EVENTS

Serious adverse event (SAE) collection begins after the patient or surrogate has signed informed consent and has received the study intervention or undergone study procedures. If a patient experiences a SAE after consent, but prior to receiving the study intervention, the event will NOT be collected unless the Principal Investigator feels the event may have

been caused by a protocol procedure. SAEs will be collected after initiation of study intervention until ICU discharge or day 28, whichever occurs first, regardless of the investigator's opinion of causation. Thereafter, SAEs are not required to be reported unless the investigator feels the events were unanticipated and related to the study procedure. If a determination is made that a SAE has a reasonable possibility of having been caused by a study procedure, it will be classified as a suspected adverse reaction. If the suspected adverse reaction is unanticipated, it will be classified as a serious unanticipated suspected adverse reaction (SUSAR).

As per the FDA and NIH definitions, a SAE is any adverse event that results in one of the following outcomes:

- Death
- A life-threatening experience (that is, immediate risk of dying)
- Prolonged inpatient hospitalization or rehospitalization

As per <https://www.fda.gov/safety/reporting-serious-problems-fda/what-serious-adverse-event> report if admission to the hospital or prolongation of hospitalization was a result of the adverse event. Emergency room visits that do not result in admission to the hospital should be evaluated for one of the other serious outcomes (e.g., life-threatening; required intervention to prevent permanent impairment or damage; other serious medically important event).

- Persistent or significant disability/incapacity

As per <https://www.fda.gov/safety/reporting-serious-problems-fda/what-serious-adverse-event> report if the adverse event resulted in a substantial disruption of a person's ability to conduct normal life functions, *i.e.*, the adverse event resulted in a significant, persistent or permanent change, impairment, damage or disruption in the patient's body function/structure, physical activities and/or quality of life.

Important medical events that may not result in death, be life threatening, or require hospitalization may be considered SAEs when, based upon appropriate medical judgment, they may jeopardize the patient and may require medical or surgical intervention to prevent one of the outcomes listed in the above definition.

### 13.3 IRB AND DSMB REPORTING

[figure not shown]
#### 13.3.1 IRB REPORTING

An AE or SAE is judged to be reportable to University of Pittsburgh HRPO, if it meets ALL of the following: i.) unanticipated in terms of nature, severity, or frequency; ii.) related or possibly related to study intervention; iii.) places subjects or others at a greater risk of physical, psychological, economic or social harm than was previously known or recognized. If the AE is judged to be reportable to the IRB based on above criteria, then the study team at the University of Pittsburgh will report to the HRPO within 10 working days. If it is an SAE and meets the above criteria, the study team will report to the HRPO within 24 hours.

All SAEs that meet above criteria and occurring at Mayo Clinic must be reported to the study team at University of Pittsburgh within 24 hours. All AEs that meet above criteria and occurring at Mayo Clinic must be reported within 5 working days to the team at University of Pittsburgh. The study team at University of Pittsburgh will then report all AE and SAE to the University of Pittsburgh HRPO within timelines shown in Table 7. The AEs that comprise the safety outcomes will be included in outcome reporting and will not be reported a second time as AEs or SAE.

At both clinical sites the study personnel must alert the Principal Investigator of any serious and study procedure-related adverse event within 24 hours of investigator/coordinator awareness of the event. Please note that most AEs will not meet the definition of an Unanticipated Problem Involving Risk to Subjects or Others and need not be reported to the HRPO. Expected AEs or AEs which are determined by the investigator to be unrelated to the research intervention need not be reported to the IRB. The flow chart below provides an algorithm for determining whether an AE meets the definition of an unanticipated problem involving risk to subjects or others and whether it needs to be reported to HRPO.

